13.8 Appendix 8 Subject Accrual Order During Dose Escalation

Selected examples shown through dose selection in each Arm. Accrual of six subjects in cohorts prior to expansion is not shown. Each square represents 1 subject with dose level indicated by number. Symbol “*” indicates DLT. Symbol “•” indicates dose escalation decision.

1. No DLT observed

Arm 1	1	1	1	•	2	2	2	•	3	3	3			
Arm 2	1	1	1	•	2	2	2	•	3	3	3			

2. No DLT observed, Arm 1 accrual slower

Arm 1	1	1		•	2			•	3	3		3		
Arm 2	1	1	1	•	2	2	2	•	3	3	3			

3. Single DLT in Arm1, DL2

Arm 1	1	1	1	•	2	2	2*	2	2	2	•	3	3	3
Arm 2	1	1	1	•	2	2		2	•	3	3	3		

4. Single DLT in Arm1 DL2, Arm 1 accrual slower

Arm 1	1	1		•	2*	2	2	2	2	2	•	3		3	3
Arm 2	1	1	1	•	2	2	2	•	3	3	3				

5. Single DLT in Arm 2, DL2

Arm 1	1	1	1	•	2	2	2	•	3	3	3			
Arm 2	1	1	1	•	2	2*	2	2	2	2	•	3	3	3

6. MTD reached in Arm 1, DLT seen in 2/5 subjects at DL2†

Arm 1	1	1	1	•	2	2*	2	2	2*					
Arm 2	1	1	1	•	2		2	2						

7. MTD reached in Arm 2, DLT seen in 2/2 subjects at DL2

Arm 1	1	1	1	•	2	2	2	•	3	3	3			
Arm 2	1	1	1	•		2*	2*							

8. MTD reached in Arm 2, DLT seen in 2/3 subjects at DL2, Arm 1 accrual slower

Arm 1	1			•	2	2		2	•	3	3		3	
Arm 2	1	1	1	•	2*	2	2*							

† In Example #6 above, the MTD for subjects in Arm 1 is reached at a dose lower than the dose under evaluation in Arm 2. Accruing subjects in the order of Example #6 is not expected, because the risk of severe or serious adverse events after cell therapy is correlated with a subject’s tumor burden ([Garcia-Manero et al, 2015](#); [Garzon et al, 2017](#)). If, as in Example #6, the MTD for Arm 1 is reached at or below the dose under investigation in Arm 2, enrollment in Arm 2 will be paused and data reviewed by the Principal Investigators, Sponsor, and the DMC.

DL = dose level; DLT = dose-limiting toxicities; MTD = maximum tolerated dose

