6.2.1.3 Dose Escalation and Dose Reduction Decisions

If none of the initial dose evaluation group subjects experience a DLT, subjects in the treatment phase who have not yet received NTLA-5001 and subsequent subjects entering the treatment phase will be eligible for the next dose escalation cohort.

If 1 of the initial dose evaluation group subjects experiences a DLT, enrollment will continue in the dose evaluation group for 3 additional subjects. When the last subject in the expanded dose evaluation group has been observed through Day 28:

- If no subject in the expanded dose evaluation group experiences a DLT, subjects in the treatment phase who have not yet received NTLA-5001 and subsequent subjects entering the treatment phase will be eligible for the next dose escalation cohort.
- If 1 or more additional subject in the expanded dose evaluation group experiences a DLT, no dose escalation will be proposed. Subjects in the treatment phase who have not yet received NTLA-5001 and subsequent subjects entering the treatment phase will be eligible for Dose Level -1 if DLTs are seen at Dose Level 1, or the next lower dose level will be declared the maximum tolerated dose (MTD), if DLTs are seen at Dose Level 2 or 3. Fewer than 2/6 subjects with DLTs will establish the MTD.

If 2 or 3 of the initial dose evaluation group experiences a DLT, no dose escalation will be proposed. Subjects in the treatment phase who have not yet received NTLA-5001 and subsequent subjects entering the treatment phase will be eligible for Dose Level -1 if DLTs are seen at Dose Level 1, or the next lower dose level will be expanded to 6 subjects if DLTs are seen at Dose Level 2 or 3. Fewer than 2/6 subjects with DLTs will establish the MTD.

If a dose escalation is proposed, the subsequent cohort dose may be reduced or increased by up to 50% if the Sponsor and investigator agree, based on observations in the prior cohort. At the Sponsor's discretion, up to 6 subjects may be enrolled in any dose cohort for Arm 1 or Arm 2.

If a subject receiving out-of-specification cells has a DLT, this finding would not be attributed to DLT tally for a specific Dose Level; but would be reviewed as part of the overall safety profile in conjunction with planned safety reviews and by the Sponsor, investigators, and DMC. The event would be considered when making dose escalation decisions, stopping rule decisions, and/or dose selection for expansion cohort.

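### If Arm 1 fails at Dose Level 1, no Arm 2 pause is stated, because the Appendix 8 trigger needs an Arm 1 MTD that Section 6.2.1.3 does not yet name

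*Protocol*

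**What the plan says.** Section 6.2.1.1 has the two arms escalate independently and points to Section 13.8 for accrual order. The footnote to Example 6 there sets the cross-arm rule: if "the MTD for Arm 1 is reached at or below the dose under investigation in Arm 2, enrollment in Arm 2 will be paused", and the Principal Investigators, Sponsor and DMC review the data.

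Section 6.2.1.3 says what follows when a dose level fails:

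- One DLT in the initial group and at least one more after expansion, at Dose Level 2 or 3: "the next lower dose level will be declared the maximum tolerated dose (MTD), if DLTs are seen at Dose Level 2 or 3".
- Two or three DLTs in the initial group, at Dose Level 2 or 3: "the next lower dose level will be expanded to 6 subjects if DLTs are seen at Dose Level 2 or 3".
- Either pattern at Dose Level 1: remaining subjects "will be eligible for Dose Level -1 if DLTs are seen at Dose Level 1".
- Both failure rules end with the same condition: "Fewer than 2/6 subjects with DLTs will establish the MTD".

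Three Appendix 8 headings show how that appendix uses the word *reached*: Example 6 ("MTD reached in Arm 1, DLT seen in 2/5 subjects at DL2"), Example 7 ("MTD reached in Arm 2, DLT seen in 2/2 subjects at DL2") and Example 8 ("MTD reached in Arm 2, DLT seen in 2/3 subjects at DL2"). None of the eight examples shows a DLT at Dose Level 1.

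**The concern.** The pause is mandatory and names its reviewers, but it depends on an Arm 1 MTD existing. Failure of the starting dose in Arm 1 is the case where the text supplies none: no lower level has yet been tested, and Section 6.2.1.3 simply moves Arm 1 down. Sections 6.2.1.4 and 13.8 both say that risk rises with tumor burden, so a dose with two DLTs in the low-burden arm is a warning for Arm 2. At stake is whether Arm 2 subjects can be dosed at or above that level before anyone is required to stop and decide.

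**Working it through.** **1. Arm 1 failure paths against the trigger.**

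| Arm 1 failure | Section 6.2.1.3 | Appendix 8 | Arm 2 pause? |
|---|---|---|---|
| Dose Level 2 or 3: 1 DLT, then at least 1 more after expansion | Next lower level declared the MTD | Example 6 | Yes |
| Dose Level 2 or 3: 2 or 3 DLTs in the initial group | Lower level expanded to 6; fewer than 2/6 establishes the MTD | Examples 7 and 8 (both Arm 2) call it reached at once | Yes on Appendix 8 usage; Section 6.2.1.3 times the MTD differently |
| Dose Level 1: either pattern | Move to Dose Level -1; no MTD named | No example | Not stated |

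The third row is the gap. Both arms start at Dose Level 1 (Section 4.1.3), so an Arm 2 cohort at Dose Level 1, 2 or 3 is at or above the failed dose.

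**2. Time until an MTD can be named after Dose Level 1 fails.** Inputs: each of the first 3 subjects at a level is observed for 28 days before the next is enrolled (Section 6.2.1.1); fewer than 2/6 establishes the MTD (Section 6.2.1.3). I assume that the stagger applies at Dose Level -1, that subjects 4 to 6 are dosed together, and that accrual is immediate. With n subjects (n ≤ 3) already observed at the lower level:

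days to 6 observed = 28 × (3 − n) + 28

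For a new Dose Level -1 cohort, n = 0: 28 × 3 + 28 = 112 days. Slower accrual lengthens this. If Dose Level -1 also fails, no MTD is ever named.

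**3. Whether another rule forces a halt.** I compared the 7 DLT categories in Section 6.2.1.2 with the pausing criteria in Section 6.2.1.5:

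- Always covered (2): GVHD and related death.
- Partly covered (2): CRS and ICANS, only if Grade 4 and not resolved to Grade 1 within 72 hours, or fatal.
- Covered only if fatal (3): infusion reaction, prolonged cytopenia and organ toxicity.

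The total is 2 + 2 + 3 = 7. Two non-fatal Grade 3 ICANS events at Dose Level 1 therefore fail the level and meet no pausing criterion.

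The Section 6.2.1.1 review covers DLT data from both arms. It takes place once a dose evaluation group has completed 28 days, its purpose is to consider escalation, and the DMC is not among its required participants. It does not close an open cohort in the other arm.

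**4. Arm 2 exposure meanwhile.** The first 3 Arm 2 subjects at a level are spaced by 28 days, so about 1, 2 and 3 could be dosed within 28, 56 and 84 days. Subjects 4 to 6, if the cohort is expanded, are not staggered. The cohort cap is 6, so with k already dosed at most 6 − k remain, and Arm 2's own DLT rules still apply.

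**5. How often Arm 1 might fail Dose Level 1.** The documents give no DLT rate, so the rate p is assumed. With an initial group of 3, P(fail) = P(X ≥ 2 of 3) + P(X = 1 of 3) × P(Y ≥ 1 of 3):

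- p = 0.10: 0.028 + 0.066 = 0.094
- p = 0.20: 0.104 + 0.187 = 0.291
- p = 0.33: 0.255 + 0.311 = 0.566

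This is not the probability that the gap matters. That also requires Arm 2 to be enrolling and the DLTs to fall outside Section 6.2.1.5.

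**The case against.** The strongest reply is that Appendix 8 calls the MTD reached as soon as a level has two DLTs. On that usage, two Arm 1 DLTs at Dose Level 1 put the MTD below Dose Level 1, hence below any Arm 2 dose from Dose Level 1 up, and the pause applies at once. This is a sensible reading and probably what the sponsor would do. But it extends labels from Dose Level 2 examples, where a lower level had already been given, to a case where none had been tested. Section 6.2.1.3 does not declare an MTD there. A first-in-human safety rule should not rest on that inference.

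The same reply does settle failures at Dose Level 2 or 3. A reader might infer from Section 6.2.1.3 that two or three initial-group DLTs delay the pause by 28, 56 or 84 days (the formula above with n = 3, 2 or 1 at the lower level). Examples 7 and 8 sit in the appendix that contains the pause rule, and they call this pattern reached immediately. Nothing suggests that the word means something else for Arm 1. If the lower level already has 6 subjects with fewer than 2 DLTs, there is no delay on either reading.

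It is also fair to say that Arm 2 is not unwatched. Its own escalation needs a review that includes Arm 1 DLTs, the DMC reviews safety data periodically and may be consulted at any time, and the DMC Charter, which is not among these documents, may add more. What is missing is an automatic halt of an open cohort with required DMC input, not review altogether.

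**Conclusion.** The point holds for failure of Dose Level 1 in Arm 1. On the literal text no Arm 2 pause is triggered until Dose Level -1 yields an MTD. That takes at least 112 days for a new cohort of 6 under the stagger, and never happens if that level fails too. The size rests on equating *reached* with the MTD being established under Section 6.2.1.3, and on the accrual assumptions above.

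At Dose Levels 2 and 3 the documents support only a wording inconsistency: Appendix 8 treats the MTD as reached at once, while Section 6.2.1.3 establishes it after the lower level is expanded to 6. Nor do they support reading the gap as leave for Arm 2 to escalate without sight of the Arm 1 DLTs, since Section 6.2.1.1 requires that review.

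No probability is claimed that the situation would have arisen. The protocol describes the Example 6 ordering as not expected, and SAP Section 7 records that only 2 subjects received NTLA-5001 before termination. This concerns the design as written, and correcting it is a cheap improvement.

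**What to change.** Reword the Appendix 8 footnote so that the trigger is a DLT count, and repeat it in Section 6.2.1.3 or as a separate Arm 2-only paragraph in Section 6.2.1.5:

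> If 2 or more Arm 1 subjects at the same dose level have a DLT and Arm 2 is enrolling at that dose level or higher, Arm 2 enrollment is paused at the second DLT pending review by the Principal Investigators, Sponsor and DMC, whether or not an Arm 1 MTD has been established; Arm 1 continues per 6.2.1.3.

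It should not become another bullet in the Section 6.2.1.5 list. That list suspends enrollment generally, so a bullet there could also stop Arm 1 from moving to Dose Level -1. The present wording can stay for Arm 2 enrolling at the Arm 1 MTD itself.

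The same sentence resolves the inconsistency at Dose Levels 2 and 3. It needs no new data, subjects or procedures. The downside is an Arm 2 pause that is temporary and starts sooner than on the literal text.

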1 VERSION HISTORY

This SAP for Protocol ITL-5001-CL-001 is based on the protocol version 2.0 dated 22 December 2021.

Table 1 Summary of Changes

Version/ Date	Associated Protocol Amendment	Rationale	Specific Changes
1.0 / 06 January 2023	2.0 / 22 December 2021	N/A	N/A

2 INTRODUCTION

This statistical analysis plan (SAP) provides the detailed methodology for summary and statistical analyses of the data collected in Study ITL-5001-CL-001. This document may modify the plans outlined in the protocol. Details will be included in Section 7.

2.1 Objectives and Endpoints

OBJECTIVES	ENDPOINTS
Primary	

 Dose escalation: To identify dose for use in the expansion cohorts Dose expansion: To evaluate the safety and tolerability of NTLA-5001 in subjects with AML and blasts <5% of bone marrow (Arm 1) and in subjects with AML and blasts ≥5% of bone marrow (Arm 2) 	
 safety and tolerability as determined by AEs dose-limiting toxicities (DLTs) (dose escalation only)
Secondary	

 To characterize the cell kinetics (CK) of NTLA-5001 in peripheral blood To estimate the anti-tumor activity of NTLA-5001 in subjects with AML 	
 frequency and persistence of NTLA-5001 according to the TCR transgene copy number (via droplet digital polymerase chain reaction [ddPCR]) Disease response (including measurable residual disease [MRD] response), duration of response/ remission, event free survival and time to disease progression
Exploratory	

 To estimate other cancer-related outcomes in subjects with AML To characterize subject AAV exposure To characterize immunologic parameters and characteristics of NTLA-5001 cells after administration in subjects with AML 	
 overall survival Eastern Cooperative Oncology Group (ECOG) performance status QOL as measured by the European Organization for Research and Treatment of Cancer Quality of Life Questionnaire (EORTC QLQ-C30) instrument and length of hospital stay after NTLA-5001 infusion presence of adenovirus vector in blood and urine plasma cytokine levels WT1 expression on tumor NTLA-5001 characteristics including flow cytometry, phenotype, editing, and gene expression bone marrow immune parameters and NTLA-5001 cell kinetics

2.2 Study Design

This is Phase 1/2a, first-in-human, single-dose study to investigate NTLA-5001 in subjects with Acute Myeloid Leukemia (AML). The design is according to guidance for first-in-human trials and for the investigation of advanced therapy medicinal products, including the European Medicine Agency “Guideline on strategies to identify and mitigate risks for first-in-human and early clinical trials with investigational medicinal products”; and draft guidance “Guideline on quality, non-clinical and clinical requirements for investigational advanced therapy medicinal products in clinical trials”; and the FDA draft guidance “Acute Myeloid Leukemia: Developing Drugs and Biological Products for Treatment”. The design is to ensure the safety and well-being of trial subjects and to mitigate risk to the greatest extent possible.

This study consists of 2 phases: dose escalation and dose expansion. A subject that meets all inclusion and none of the exclusion criteria will be enrolled into the leukapheresis phase in Arm 1 for subjects with AML blasts <5% of bone marrow or in Arm 2 for subjects with AML blasts \geq 5% of bone marrow. During screening, MRD will be measured in bone marrow by central laboratory assessment. After study entry, subjects may have repeat BM assessment prior to Arm assignment based on whether screening biopsy was prior to study consent, interval since screening study, change in condition, or bridging therapy. If an Arm 1 subject is found to have \geq 5% bone marrow blasts at repeat BM assessment prior to the administration of lymphodepleting chemotherapy, the subject may be re-assigned to Arm 2 or, if Arm 2 is not yet enrolling subjects, the subject may receive NTLA-5001 at Dose Level -1.

[figure not shown]
The dose escalation phase of the study will consist of up to 3 cohorts of subjects in Arm 1 and 3 cohorts of subjects in Arm 2. Each Arm 1 cohort will include up to 6 subjects, as detailed in dose escalation below. Each Arm 2 cohort will include 3 to 6 subjects. Once a dose is identified for detailed assessment of safety in Arm 1 subjects and 6 subjects have been enrolled at that dose, an expansion cohort will be opened for an additional 9 subjects in Arm 1. Once a dose is identified for detailed assessment of safety in Arm 2 subjects, a safety expansion cohort will be opened for an additional 9 subjects in Arm 2.

Each subject will undergo leukapheresis for collection of peripheral blood mononuclear cells (PBMC). [REDACTED] After leukapheresis, subjects who meet criteria for treatment and who have manufactured NTLA-5001 that meet release requirements will enter the treatment phase for the administration of lymphodepleting chemotherapy and study medication.

Each subject in the treatment group will receive lymphodepleting chemotherapy on Day -5, -4, and -3. A subject will be administered a single dose of NTLA-5001 on Day 0. Subjects will be observed in hospital for a minimum of 7 days following dosing, and subjects must remain within 2 hours of the location of the trial site to receive any needed follow up assessments or care until Day 14. UK subjects will be observed in hospital for a minimum of 14 days following dosing. Additional visits will take place at Week 2, 4, 8, and 16, then at 12-week intervals through Week 112 or until the subject is no longer receiving clinical benefit. Subjects who are no longer receiving clinical benefit will continue to be followed with clinic visits to assess subject survival and AEs every 12 weeks until 112 weeks after administration of NTLA-5001. After participating

in this study, all subjects will be followed as part of a long-term monitoring program per local and national regulations. All subjects will be followed for a minimum of 5 years in the UK and for a minimum of 15 years in the US.

Figure 1 Study Schema

DLT = dose limiting toxicities

3 STATISTICAL HYPOTHESES AND SAMPLE SIZE DETERMINATION

3.1 Statistical Hypotheses

There is no statistical hypothesis for the study.

3.2 Sample Size Determination

No formal sample size calculation was performed for this study.

Dose escalation will consist of up to 3 dose escalation cohorts in each of 2 Arms. Each Arm 1 cohort will include up to 6 subjects. Each Arm 2 cohort will include 3 to 6 subjects. Therefore, up to 36 evaluable subjects are anticipated to be enrolled in this portion of the study.

Once a dose is identified for detailed safety assessment in an Arm, a safety expansion cohort will be opened for up to 9 additional subjects to be dosed at that dose level. Thus, up to a total of 18 subjects will be dosed in safety expansion cohorts across the 2 Arms.

4 ANALYSIS SETS

For purposes of analysis, the following analysis sets are defined in [Table 2](#).

Table 2 **Analysis Sets**

Population	Description
Enrolled Set	All subjects who meet all inclusion/exclusion criteria
DLT Evaluable Set	All subjects who receive NTLA-5001 and either experience DLT(s) regardless of whether a full dose was administered or receive the full assigned dose without DLTs and complete Day 29 assessments. Subjects without DLTs who do not receive the full dose of NTLA-5001 as per their assigned dose cohort or did not complete Day 29 assessments are not evaluable for DLTs.
Full Analysis Set (FAS)	All subjects who undergo leukapheresis
Safety Analysis Set	All subjects who receive NTLA-5001
Cell Kinetics (CK) Analysis Set	All subjects who receive NTLA-5001 and have at least one evaluable CK sample

5 GENERAL METHODOLOGY AND CONVENTIONS

Qualitative/categorical data will be summarized by frequency counts and percentages. Unless otherwise specified, the calculation of proportions will be based on the sample size of the population of interest. Counts of missing observations will be included in the denominator and presented as a separate category.

Continuous variables will be summarized using descriptive statistics ie, number of non-missing values and number of missing values [ie, n (missing)], mean, median, standard deviation, minimum, maximum and first and third quartile (Q1 and Q3).

5.1 Data Handling

5.1.1 Data Cutoff Date

Data after the cutoff date may not undergo the cleaning process and will not be displayed in any listings or used for summary statistics, statistical analyses or imputations.

5.1.2 Data Handling Rules

Unless otherwise noted, values reported as greater than or less than some quantifiable limit (e.g., “< 1.0”) will be summarized with the sign suppressed in summary tables and figures, using the numeric value reported. Data will display on subject listings to include the sign.

5.2 Definition of Study Day

The study day for assessments occurring on or after the start of NTLA-5001 infusion will be calculated as:

$$\text{Study day} = \text{Date of the assessment/event} - \text{start date of NTLA-5001 infusion} + 1.$$

The study day for assessments occurring prior to the start of NTLA-5001 infusion (eg, baseline characteristics, medical history) will be negative and calculated as:

$$\text{Study day} = \text{Date of the assessment/event} - \text{start date of NTLA-5001 infusion}.$$

The study day will be displayed in all relevant data listings.

5.3 Definition of Baseline

Baseline is defined as the last measurement prior to the initiation of lymphodepleting chemotherapy.

If an assessment is planned to be performed prior to beginning lymphodepletion in the protocol and the assessment is performed on the same day as the first administration of lymphodepleting chemotherapy, it will be assumed that it was performed prior to the beginning of lymphodepletion.

Unscheduled assessments will be used in the determination of baseline. However, an unscheduled assessment performed on the day of the first administration of lymphodepleting chemotherapy will be considered to have been obtained after lymphodepletion started and therefore will not be used for baseline determination.

5.4 Safety Reporting Period

The safety reporting period is defined as the time from the date of NTLA-5001 infusion through the end of the study or (start date of new anticancer therapy – 1 day).

Note that the safety reporting period will be used for all safety analyses.

5.5 Reporting Conventions

The following conversion factors will be used to convert days into weeks, months or years:
1 week = 7 days, 1 month = 30.4375 days, 1 year = 365.25 days.

For reporting conventions, minimum and maximum values will be presented with the same decimal precision as collected in the raw data; mean, median, and quartiles should generally be presented to 1 more decimal place than the raw data; standard deviation should be displayed to 2 more decimal places than the raw data. P Non-zero percentages will be rounded to whole numbers for all populations smaller than 100 subjects, to 1 decimal place if a population includes ≥ 100 subjects. The rounding will be performed to closest integer/first decimal using the common mid-point between the two consecutive values. For example, 5.1 to 5.4 will be rounded to an integer of 5, and 5.5 to 5.9 will be rounded to an integer of 6.

Missing statistics, eg, when they cannot be calculated, should be presented as 'ND' for not done and 'NA' for not applicable. For example, if N=1, the measure of variability cannot be computed and should be presented as 'NA'.

